Section Number and Name	Description of Change	Brief Rationale	Substantial or Non-substantial
Section 4.1 Overall design; Table 2, footnotes; Section 7.1.1 Follow-up of patients post- discontinuation of study treatment; Section 7.1.2 Follow-up for survival	The minimum expected safety follow-up period of 90 days following the last dose of durvalumab for patients treated with the study treatment has been detailed and clarified, and accordingly new sections (Section 7.1.1 and 7.1.2) were added.	Text related to follow-up of patients after discontinuation of study treatment has been clarified.	Non-substantial
Section 4.4; Section 6.1.3 Duration of treatment and criteria for treatment through progression	A new section as “Continued access to study treatment” was added.	To clarify initial intent to allow continuation of the treatment with durvalumab for patients who may benefit from it, based on investigator’s opinion, after the individual patient reached end of scheduled visits, but before the study reached last patient last visit/final DCO date.	Non-substantial
Synopsis; Section 1.3 Schema; Section 9.2 Sample size estimate	Details related to sample size update were included.	To aid patient recruitment, details about the adequate sample size were included.	Non-substantial
Section 9.5 Statistical analysis	Details related to data analysis (DCO for the primary analysis) were added.	To aid patient recruitment, details were included.	Non-substantial
Section 4.4	Clarified definition of the end of study according to European Union and Food and Drug Administration requirements.	For consistency and alignment in terms of posting study results.	Non-substantial

Section Number and Name	Description of Change	Brief Rationale	Substantial or Non-substantial
Section 6	Updated the definition for “study treatments” and details of durvalumab in Table 5. Also updated text describing administration of study treatment.	For consistency and alignment with regulatory requirements.	Non-substantial
Section 8.4.1	Updated text pertaining to reporting of SAEs when EDC system is not available/temporarily not accessible. Also specified the reference document for definition of expectedness/listedness.	Updated to comply with regulatory requirements.	Non-substantial
Section 8.4.3	Specified timelines for providing relevant information to the AstraZeneca Patient Safety data entry site.	Updated to comply with regulatory requirements.	Non-substantial

1 PROTOCOL SUMMARY

1.1 Schedule of activities

The procedures for the screening and treatment periods in this study are presented in [Table 1](#), and the procedures for the follow-up period are presented in [Table 2](#).

Whenever vital signs and blood draws are scheduled for the same nominal time, the assessments should occur in the following order: vital signs and then blood draws. The timing of the vital signs assessments should be such that it allows the blood draw to occur at the timepoints indicated in the schedule of activities (SoA; [Table 1](#) and [Table 2](#)). Whenever electrocardiograms (ECGs), vital signs, and blood draws are scheduled for the same nominal time, the assessments should occur in the following order: ECG, vital signs, and then blood draws. The timing of the first 2 assessments should be such that it allows the blood draw to occur at the timepoints indicated in the SoAs ([Table 1](#) and [Table 2](#)).

- Patients may delay dosing under certain circumstances.
 - Dosing may be delayed per the Dosing Modification and Toxicity Management Guidelines (see [Section 8.4.5.1](#)), due to either immune-mediated adverse events (imAEs) or non-imAEs.
 - If dosing must be delayed for reasons other than treatment-related toxicity, dosing will resume as soon as feasible.
 - Dosing intervals of subsequent cycles may be shortened as clinically feasible in order to gradually align treatment cycles with the schedule of tumor efficacy (Response Evaluation Criteria in Solid Tumors [RECIST]) and patient-reported outcomes (PRO) assessments. Subsequent time between 2 consecutive doses cannot be less than 22 days, based on the half-life of durvalumab (see the current Investigator's Brochure [IB] for durvalumab).

One cycle of treatment with durvalumab is equal to 28 calendar days.

If imaging procedures were performed for alternate reasons prior to signing consent, these can be used for screening purposes with consent of the patient. However, all screening imaging results must have been obtained within 28 days prior to the first dose.

PRO and tumor efficacy (RECIST) assessment dates are not affected by dose delays and remain as originally scheduled, as they are based on the date of the first dose (not the date of therapy).

All other scheduled assessments must be performed relative to the start of the dosing cycle such that all laboratory procedures, etc, required for dosing should be performed within 3 calendar days prior to dosing.

Table 1 Schedule of activities for screening and treatment period

	Screening	C1 ^a	C2 ^a	C3 ^a	C4 ^a	C5 to C13 or PD (12 months) ^a	For details, see Section	
Week	-4 to -1	0	q4w ± 3 days unless dosing needs to be held for toxicity reasons					
Day	-28 to -1	1 ^a	q28d ± 3 days unless dosing needs to be held for toxicity reasons					
Informed Consent								
Informed consent: study procedures ^b	X						5.1	
Consent: genetic sample and analysis (optional)	X						5.1	
Study procedures								
Physical exam (full)	X						8.2.2	
Targeted physical exam (based on symptoms)		X	X	X	X	X	8.2.2	
Assessment of early toxicities (phone call) ^c		X	X	X			8.2.5	
Vital signs (temperature, respiration rate, blood pressure, and pulse), body weight, and height) ^d	X	X	X	X	X	X	8.2.3	
ECG ^e	X	As clinically indicated					8.2.4	
Concomitant medications	<----->						6.4	
Demography, including baseline characteristics and tobacco use	X						5.1	
Pulmonary function testing (FEV ₁) ^f	X						8.2.7	
Eligibility criteria	X	X					5.1, 5.2	
Laboratory Assessments								
Clinical chemistry ^g	X	X ^h	X	X	X	X	Table 8	
Hematology ^g	X	X ^h	X	X	X	X	Table 9	
Coagulation		X ⁱ	As clinically indicated				Table 9	
TSH ^j , (reflex free T3 or free T4 ^k)	X	X	X	X	X	X	Table 8	

	Screening	C1 ^a	C2 ^a	C3 ^a	C4 ^a	C5 to C13 or PD (12 months) ^a	For details, see Section		
Week	-4 to -1	0	q4w ± 3 days unless dosing needs to be held for toxicity reasons						
Day	-28 to -1	1 ^a	q28d ± 3 days unless dosing needs to be held for toxicity reasons						
Urinalysis	X	As clinically indicated						Table 10	
Hepatitis B and C, HIV, and tuberculosis ¹	X							8.2.1	
Pregnancy test ^m	X	X	X	X	X	X		8.2.1	
Monitoring									
WHO/ECOG performance status	X	X	X	X	X	X		8.2.6	
AE/SAE assessment ⁿ	<----->							8.3	
Drug accountability		X	All visits					6.3	
IP administration									
Durvalumab ^o		X	X	X	X	X		6.1.1.1, 6.1.2.1	
Patient-Reported Outcomes									
CCI [REDACTED]	X	X	PROs should be completed by patients prior to dosing on C1D1. Thereafter, PROs should be completed by the patients at home using a handheld device every 28 days (± 1 day), regardless of delays in dosing					8.1.2.1, 8.1.2.2, 8.1.2.3	
Biomarker assessments									
CCI [REDACTED]	X							8.8.1	
CCI [REDACTED]		X	X			C7, C9, C13 or PD		8.8.1	
CCI [REDACTED]		X ^s						8.8.1	
CCI [REDACTED]		X						8.7.1	

	Screening	C1 ^a	C2 ^a	C3 ^a	C4 ^a	C5 to C13 or PD (12 months) ^a	For details, see Section
Week	-4 to -1	0		q4w ± 3 days unless dosing needs to be held for toxicity reasons			
Day	-28 to -1	1 ^a		q28d ± 3 days unless dosing needs to be held for toxicity reasons			
Efficacy evaluations							
Tumor assessments (RECIST 1.1) ^u	X		On-study tumor assessments will begin 8 weeks ± 1 w after the first dose, then q8w ± 1 w through 48 weeks (relative to the first dose), and then q12w ± 1 w thereafter until RECIST 1.1-defined PD, plus an additional regularly scheduled follow-up scan. The on-study schedule of q8w ± 1 week (following the first assessment at 8 weeks ± 1 w after the first dose) for first 48 weeks and then q12w ± 1 w thereafter MUST be followed regardless of any delays in dosing. Additional scans can be completed per standard practice post disease progression.				8.1, Appendix F

AE = adverse event; C = Cycle; CT = computed tomography; CTCAE = Common Terminology Criteria for Adverse Event; DNA = Deoxyribonucleic acid; ECG = Electrocardiogram; ECOG = Eastern Cooperative Oncology Group; CCI

CC

66

IP = Investigational product; IFT = Liver function test; MRI = magnetic resonance imaging; PD = Progressive disease; CC = informed consent form; HAV = Human immunodeficiency virus; ICF = informed consent form.

II = investigational product, LFT = liver function test, MRI = magnetic resonance imaging, PD = progressive disease, CCI = Child's classification index, CCI = Child-Pugh classification index.

133

-10-

q12W = Every 12 weeks; q28d = Every 28 days; RECIST = Response Evaluation Criteria in Solid Tumors; SAE = Serious adverse event; SNC = single nucleotide change; T = Tumor; T = Tissue; TSH = Thyroid stimulating hormone; WHO = World Health Organization

SNP = single-nucleotide polymorphism; T_3 = Triiodothyronine; T_4 = Thyroxine; TSH = Thyroid-stimulating hormone; WHO = World Health Organization.

Note: All assessments on treatment days are to be performed prior to infusion, unless otherwise indicated.

^a These cycles refer to the administration of durvalumab.

^b Written informed consent and any locally required privacy act document authorization must be obtained prior to performing any protocol-specific procedures, including screening evaluations. All patients will be required to provide consent to supply an archival sample of their tumor. This consent is included in the main patient ICF. Informed consent of study procedures may be obtained prior to the 28-day screening window, if necessary. If laboratory or imaging procedures were performed for alternate reasons prior to signing consent, these can be used for screening purposes with consent of the patient. However, all screening laboratory results and screening imaging results must have been obtained within 28 days of the first dose.

^c Patients should be contacted every 2 weeks (± 1 day) after receiving IP during the first 3 cycles (Cycle 1 Day 14 ± 1 , Cycle 2 Day 14 ± 1 , and Cycle 3 Day 14 ± 1) to ensure early identification and management of toxicities. This contact should be documented in the medical records.

^d Body weight is recorded at each visit along with vital signs. Height is recorded at screening only. Whenever vital signs and blood draws are scheduled for the same nominal time, the assessments should occur in the following order: vital signs and then blood draws.

^e Any clinically significant abnormalities detected require triplicate ECG results. Whenever ECGs, vital signs, and blood draws are scheduled for the same

nominal time, the assessments should occur in the following order: ECG, vital signs, and then blood draws.

- f Pulmonary function testing includes FEV₁; results for up to 8 weeks prior to study enrollment are permitted.
- g Serum or plasma clinical chemistry (including LFT monitoring) and hematology may be performed more frequently if clinically indicated.
- h If screening clinical chemistry and hematology assessments are performed within 3 days prior to Day 1 (first infusion day), they do not need to be repeated at Day 1.
- i Coagulation tests are only performed at baseline on Day 1 (unless performed within 3 days prior to Day 1, in which case they do not need to be repeated) and as clinically indicated.
- j If TSH is measured within 14 days prior to Day 1 (first infusion day), it does not need to be repeated at Day 1.
- k Free T3 or free T4 will only be measured if TSH is abnormal or if there is clinical suspicion of an AE related to the endocrine system.
- l Tuberculosis testing is to be performed as needed in line with local practice.
- m For women of childbearing potential only. A urine or serum pregnancy test is acceptable. Women of childbearing potential are required to have a pregnancy test within 7 days prior to the first dose of study drug and then every 4 weeks. Pregnancy test may occur on Day 1, but results must be available and reviewed by the treating physician or Investigator prior to commencing an infusion.
- n For AEs/SAEs reported during screening, additional information such as medical history and concomitant medications may be needed.
- o Results for LFTs, electrolytes, and creatinine must be available and reviewed by the treating physician or Investigator before commencing an infusion (within 3 days).

p CCI

q CCI

r CCI

s CCI

t CCI

- u Patients will have baseline scans collected no more than 28 days before the first dose and, ideally, should be performed as close as possible to the first dose. If imaging procedures were performed for alternate reasons prior to signing consent, these can be used for screening purposes with consent of the patient. However, all screening imaging scans must have been obtained within 28 days prior to randomization. RECIST 1.1 assessments will be performed based on local institutional imaging results, using CT/MRI assessments of the chest and abdomen (including the entire liver and both adrenal glands). Additional anatomy

should be imaged based on signs and symptoms of individual patients, including new lesions at follow-up. If an unscheduled assessment was performed and the patient has not progressed, every attempt should be made to perform the subsequent assessments at their scheduled visits (relative to the date of IP treatment initiation). All confirmatory scans should be recorded in the database. For patients who are clinically stable and being treated through radiological progression, the follow-up scan performed after a RECIST 1.1-defined PD should be performed preferably at the next (and no later than the next) scheduled imaging visit, and no less than 4 weeks after the prior assessment of PD. For these patients the assessments should continue as indicated here. Special Confirmation of Radiological Progression criteria apply for tumor assessments on the follow-up scan ([Appendix F](#)).

Note: If a patient has a delay to an infusion of study drug, the efficacy and CCI should be conducted relative to the date of first dose administration.

Table 2 Schedule of activities for patients who have discontinued study drug or completed treatment with study drug

Evaluation	Time since last dose of durvalumab								For details, see Section	
	Day (± 3)	Months (± 1 week)						12 months and every 3 months (± 2 weeks)		
	30	2	3	4	6	8	10			
Physical examination (full)	X								8.2.2	
Vital signs	X								8.2.3	
Body weight	X	X	X						8.2.3	
Pregnancy test ^a	X	As clinically indicated							8.2.1	
AE/SAE assessment	X	X	X						8.3	
Concomitant medications	X	X	X						6.4	
WHO/ECOG PS ^b	At timepoints consistent with tumor assessments; at 30, 60, and 90 days after last dose; and then at initiation of subsequent anticancer therapy								8.2.6	
Subsequent anticancer therapy ^{c,d}	← →									
Survival status ^e		X	X	X	X	X	X		8.1.1	
Hematology	X	X	X						8.2.1	
Clinical chemistry	X	X	X						8.2.1	
Urinalysis	As clinically indicated								8.2.1	
TSH (reflex free T3 or free T4) ^f	X	X	X						8.2.1	
CCI [REDACTED]		X	X	X					8.1.2.1, 8.1.2.2, 8.1.2.3, 9.5.2.3	
Tumor assessment as per local institutional standard care (RECIST 1.1) ^h	Additional scans to be completed per standard practice post progression. Patients who permanently discontinue IP for reasons other than objective RECIST 1.1 disease progression should continue to have RECIST 1.1 assessments performed q8w \pm 1 week beginning 8 weeks after IP treatment initiation for the first 48 weeks (relative to the first dose) and q12w \pm 1 week thereafter until clinical progression/deterioration or RECIST 1.1-defined radiological progression plus one or more additional follow-up scans for confirmation of progression until confirmed radiological progression, the end of study, death, study discontinuation, or Sponsor decision (whichever comes first).								8.1, Appendix F	

AE = Adverse event; CT = Computed tomography; eCRF = Electronic case report form; CCI [REDACTED]

CCI

= Investigational product; IV = Intravenous; MRI = Magnetic resonance imaging; NSCLC = Non-small cell lung cancer; PD = Progressive disease; **CCI** [REDACTED]; IP

CCI

CCI [REDACTED]; q8w, q12w = Every 8, 12 weeks, respectively; RECIST 1.1 = Response Evaluation Criteria in Solid Tumors version 1.1; SAE = Serious adverse event; T3 = Triiodothyronine; T4 = Thyroxine; TSH = Thyroid-stimulating hormone; WHO/ECOG PS = World Health Organization/Eastern Cooperative Oncology Group Performance Status.

- ^a For women of childbearing potential only. A urine or serum pregnancy test is acceptable.
- ^b WHO/ECOG PS should also be collected at other site visits that the patient attends if appropriate site staff is available to collect such information. In addition, WHO/ECOG PS should be provided when information on subsequent anticancer therapy is provided, where possible.
- ^c Details of any treatment for NSCLC post the last dose of IP must be recorded in the eCRF. At minimum, collect the start date and description of the subsequent anticancer therapy.
- ^d For patients who discontinue the IP following disease progression, available readings of CT/MRI from local practice should be collected from patients' medical charts while information on subsequent anticancer treatment is collected.
- ^e Patients who decline to return to the site for evaluations should be contacted by telephone as an alternative. In addition to the regularly scheduled survival follow-up, patients may be contacted or the patient's family, or by contact with the patient's current physician in the week following data cutoff to confirm survival status. Every effort should be made to contact patients by telephone to follow and record survival status.
- ^f Free T3 or free T4 will only be measured if TSH is abnormal or if there is clinical suspicion of an AE related to the endocrine system.
- ^g **CCI** [REDACTED].
- ^h Only for patients yet to progress, RECIST 1.1 assessments will be performed on images from CT (preferred) or MRI, each preferably with IV contrast, of the chest and abdomen (including the entire liver and both adrenal glands). Additional anatomy should be image-based on signs and symptoms of individual patients. For patients who are clinically stable and being treated through radiological progression, the follow-up scan performed after a RECIST 1.1-defined PD should be performed preferably at the next (and no later than the next) scheduled imaging visit, and no less than 4 weeks after the prior assessment of PD; special Confirmation of Radiological Progression criteria apply for tumor assessments on the follow-up scan ([Appendix F](#)). If an unscheduled assessment was performed and the patient has not progressed, every attempt should be made to perform the subsequent assessments at their scheduled visits. The modality of tumor assessment should be the same throughout the study.

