4 STUDY DESIGN

4.1 Overall design

This is a Phase II open-label, single-arm, multicenter, international study to evaluate the clinical activity of durvalumab (1500 mg q4w) in patients with Stage III unresectable NSCLC who have an Eastern Cooperative Oncology Group (ECOG) PS of 0 to 2 and who were treated with radiotherapy but are ineligible for chemotherapy. Patients will be enrolled into 2 cohorts according to the dose of radiotherapy received prior to study entry (Cohort A: Standard Radiotherapy [60 Gy \pm 10% or hypofractionated BED]; Cohort B: Palliative Radiotherapy [40 to < 54 Gy or hypofractionated BED]).

Approximately 150 patients will be treated with the study drug in Europe and North America. Patients will be in CR, PR, or have SD following radiation therapy, as assessed by the Investigator and further supported by the screening imaging radiological assessment. Patients must not have progressed following radiation therapy, and radiation therapy must be completed within 6 weeks (42 days) prior to first IP dose administration. The last dose of radiation therapy is defined as the day of the last radiation treatment session.

Patients must have histologically- or cytologically-documented NSCLC and locally-advanced, unresectable Stage III disease (according to the International Association for the Study of Lung Cancer [IASLC] Staging Manual Version 8 [\[IASLC 2016\]](#)). Patients must be deemed to be ineligible for chemotherapy per Investigator assessment.

For an overview of the study design see [Figure 1](#), Section [1.3](#). For details on treatments given during the study, see Section [6.1](#) Treatments Administered.

For details on what is included in the efficacy and safety endpoints, see Section 3 Objectives and Endpoints.

Patients will receive study treatment for 12 months or until RECIST 1.1-defined radiological progression by Investigator unless there is evidence of an unacceptable toxicity, or if the patient requests to stop the study treatment. See Section 6.1.3 for detailed criteria.

Patients who have discontinued study treatment due to toxicity or symptomatic deterioration, clinical progression, or who have commenced subsequent anticancer therapy, will be followed up for AEs and with PRO-questionnaires for 90 days after study treatment discontinuation, and thereafter followed up with tumor assessments until RECIST 1.1-defined radiological PD plus an additional follow-up scan or until death (whichever comes first).

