7.1.1 Follow-up of patients post discontinuation of study treatment

All patients who discontinue the study treatment will be followed up for safety assessments (AEs) and with CCI 90 days after their last dose of study treatment and for

survival follow-up. Additional assessments to be performed at the time of the 90-day safety follow-up are detailed in the SoA ([Table 2](#)).

Patients who have discontinued study treatment prior to objective RECIST 1.1-defined radiological progression will be followed up with tumor assessments according to the SoA ([Table 2](#)) until RECIST 1.1-defined PD or death, regardless of whether or not the patient started a subsequent anticancer therapy, unless they have withdrawn all consent to study-related assessments.

Subsequent anticancer therapy (including radiation therapy) will be assessed and recorded from the end of treatment with study treatment through the safety and survival follow-up period or until death for patients who have discontinued study treatment, including at PD.

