7.1.3 Procedures for discontinuation of study treatment

Discontinuation of study treatment, for any reason, does not impact the patient's participation in the study. A patient who decides to discontinue IP will always be asked about the reason(s) for discontinuation and the presence of any AE. The patient should continue attending subsequent study visits, and data collection should continue according to the study protocol. If the patient does not agree to continue in-person study visits, a modified follow-up must be arranged to ensure the collection of endpoints and safety information. This follow-up could be a telephone contact with the patient, a contact with a relative or treating physician, or information from medical records. The approach taken should be recorded in the medical records. A patient that agrees to modified follow-up is not considered to have withdrawn consent or to have withdrawn from the study.

Patients who are permanently discontinued from further receipt of IP, regardless of the reason, will be identified as having permanently discontinued treatment. Patients who are permanently discontinued will enter follow-up (see the SoAs in [Table 1](#) and [Table 2](#)).

Patients who permanently discontinue drug for reasons other than objective RECIST disease progression should continue to have RECIST scans performed every 8 weeks (q8w) \pm 1 w for the first 48 weeks (relative to the date of the first dose), and then every 12 weeks \pm 1 w thereafter until RECIST 1.1-defined radiological PD plus an additional follow-up scan or death (whichever comes first) as defined the SoAs ([Table 1](#) and [Table 2](#)).

If a patient is discontinued for RECIST 1.1-defined progression, then the patient should have 1 additional follow-up scan performed preferably at the next (and no later than the next) scheduled imaging visit, and no less than 4 weeks after the prior assessment of PD.

All patients will be followed for survival until the end of the study.

Patients who decline to return to the site for evaluations should be contacted by telephone as indicated in the SoAs ([Table 1](#) and [Table 2](#)) as an alternative.

Patients who have permanently discontinued from further receipt of IP will need to be discontinued from the IVRS/IWRS.

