Symptomatic deterioration is not a descriptor for progression of NTLs: it is a reason for stopping study therapy and will not be included in any assessment of NTLs.

Patients with 'symptomatic deterioration' requiring discontinuation of treatment without objective evidence of disease progression at that time should continue to undergo tumor

assessments where possible until objective disease progression is observed.

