#### **3.3.1 Progression-Free Survival**

Progression-free survival is defined as the time from the date of first dose of durvalumab until the date of objective disease progression or death (by any cause in the absence of progression) regardless of whether the patient discontinues durvalumab or receives another anticancer therapy prior to progression.

- $PFS \text{ (days)} = (\text{date of PFS event or censoring}) - (\text{date of first dose of durvalumab}) + 1$ .

Patients who have not progressed or died at the time of analysis will be censored at the date of their last evaluable tumor assessment (ie, this doesn't include NE or missing value).

If the patient progresses or dies after 2 or more missed visits, the patient will be censored at the date of the latest evaluable assessment prior to the missed visits.

If the patient has no evaluable visits or does not have baseline data, he/she will be censored at Day 1 unless he/she dies within 2 visits of baseline, in which case the date of death is the event date.

Given the scheduled visit assessment scheme (i.e. eight-weekly for the first 48 weeks then twelve-weekly thereafter) the definition of 2 missed visits will change.

1. If the previous RECIST assessment is baseline then two missing visits will equate to 17 weeks since the previous RECIST assessment, allowing for a late visit (i.e.  $2 \times 8$  weeks + 1 week for a late assessment = 17 weeks).
2. If the previous RECIST assessment is post baseline and less than study day 274 (i.e. week 39) then two missing visits will equate to 18 weeks since the previous RECIST assessment, allowing for early and late visits (i.e.  $2 \times 8$  weeks + 1 week for an early assessment + 1 week for a late assessment = 18 weeks).
3. If the two missed visits occur over the period when the scheduled frequency of RECIST assessments changes from eight-weekly to twelve-weekly this will equate to 22 weeks (i.e. take the average of 8 and 12 weeks which gives 10 weeks and then apply same rationale, hence  $2 \times 10$  weeks + 1 week for an early assessment + 1 week for a late assessment = 22 weeks). The time period for the previous RECIST assessment will be from study days 274 to 344 (i.e. week 39 to week 49).
4. From week 49 onwards (when the scheduling changes to twelve-weekly assessments), two missing visits will equate to 26 weeks (i.e.  $2 \times 12$  weeks + 1 week for an early assessment + 1 week for a late assessment = 26 weeks).

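### Protocol Table 2 can be read as ending RECIST scans at clinical progression, contrary to the rest of the plan; where sites do so, PFS and duration of response are biased upward

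*Protocol*

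**What the plan says.** **The row in question.** Protocol Table 2 (section 1.1) covers patients off drug. Those who stopped for a reason other than RECIST progression are scanned every 8 weeks to Week 48 and every 12 weeks after that, "until clinical progression/deterioration or RECIST 1.1-defined radiological progression plus one or more additional follow-up scans for confirmation of progression". The same sentence then has a second stop clause: "until confirmed radiological progression, the end of study, death, study discontinuation, or Sponsor decision (whichever comes first".

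**The rest of the protocol.** Section 4.1, like the synopsis, names the group: "Patients who have discontinued study treatment due to toxicity or symptomatic deterioration, clinical progression, or who have commenced subsequent anticancer therapy". After 90 days of safety follow-up these patients are "and thereafter followed up with tumor assessments until RECIST 1.1-defined radiological PD plus an additional follow-up scan or until death". Section 7.1.1 scans patients "until RECIST 1.1-defined PD or death, regardless of whether or not the patient started a subsequent anticancer therapy", and section 7.1.3 scans "until RECIST 1.1-defined radiological PD plus an additional follow-up scan or death (whichever comes first) as defined the SoAs". Both sections cite Table 2 as their schedule, and section 8 makes adherence to Tables 1 and 2 a requirement. Appendix F keeps patients with symptomatic deterioration under assessment, subject to clinical feasibility.

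**The SAP.** Section 3.1.1.2 says that patients with symptomatic deterioration should continue "assessments where possible until objective disease progression is observed". Section 3.3.1 counts only objective progression or death as a PFS event, and censors a patient with neither at the last evaluable tumor assessment. It adds: "If the patient progresses or dies after 2 or more missed visits, the patient will be censored", with the censoring date put back to the last evaluable assessment before the gap. Section 3.3.5 takes the end of response from the PFS date. The only PFS sensitivity analysis, in section 4.4.1, concerns COVID-19 deaths.

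**The concern.** Table 2 is the page that sites work from. A site that takes its first clause at face value stops scanning a patient who has declined clinically but has no RECIST progression. From then on only death can give that patient a PFS event, and only if it comes soon enough. Otherwise the patient is censored at a scan taken shortly before progression was likely to show. Kaplan-Meier treats such a patient as having the same outlook as those still being scanned, which is unlikely to be true.

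At stake are the secondary estimates: median PFS, PFS6, PFS12 and duration of response. The study has one arm, so no comparator carries the same bias, and it passes straight into the reported figures. Sites that follow Table 2 and sites that follow section 7.1.3 would also produce data that are not comparable. Scans that were not done cannot be recovered later.

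**Working it through.** **1. The stop rules side by side** (patients off drug without RECIST progression)

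| Place | Scans continue until | Clinical progression or deterioration |
|---|---|---|
| Protocol Table 2, first clause | clinical or radiological progression plus confirmation | is a stop |
| Protocol Table 2, second clause | confirmed radiological progression, end of study, death, study discontinuation or Sponsor decision | not listed |
| Synopsis and Protocol 4.1 | RECIST progression plus one scan, or death | both named; scanning continues |
| Protocol 7.1.1 | RECIST progression or death | not named; covered as any pre-progression stop |
| Protocol 7.1.3 | RECIST progression plus one scan, or death | not named; covered as any non-RECIST stop |
| Appendix F, SAP 3.1.1.2 | assessment continues (SAP: to objective progression) | symptomatic deterioration named; if feasible or possible |

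**2. The SAP windows, reproduced.** Two missed visits equal:
- from baseline: 2 × 8 + 1 = 17 weeks;
- from a post-baseline scan before Day 274: 2 × 8 + 1 + 1 = 18 weeks;
- across the schedule change: 2 × 10 + 1 + 1 = 22 weeks;
- from Week 49: 2 × 12 + 1 + 1 = 26 weeks.

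These agree with SAP 3.3.1. The plan gives no event count, power or precision for PFS. Its only precision figures (Protocol Table 11) concern the primary safety endpoint, and this point does not touch them.

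**3. One patient followed through (illustrative weeks).** The last evaluable scan is at Week 16, clinical progression is at Week 20, and the next scheduled scan is at Week 24. The window closes at Week 16 + 18 = Week 34.
- Scanning continued, progression seen at Week 24: event at Week 24.
- Scanning stopped, death at Week 30 (14 weeks after the scan): event at Week 30, later than Week 24.
- Scanning stopped, death at Week 40 (24 weeks after the scan): censored at Week 16.
- Scanning stopped, alive at the cut-off: censored at Week 16.

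Both changes, the later event date and the lost event, raise the PFS curve.

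**4. Size, by simulation.** PFS was simulated with 20,000 patients per scenario, using the SAP scan schedule and windows. Scanning to RECIST progression or death was compared with scanning stopped at clinical progression.

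Median PFS was set at 5.6, 11 or 16.8 months. The outer values are the placebo and durvalumab medians quoted in Protocol 2.3.1; 11 is an assumed midpoint. The other inputs are assumptions not found in the documents:
- 5, 10, 20 or 30% of patients progress clinically first;
- RECIST progression follows after a mean of 6 weeks;
- median survival after progression is 3, 6 or 12 months;
- times are exponential, with a common cut-off at Week 130.

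This gives 3 × 4 × 3 = 36 scenarios.

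| Quantity | Change when scans stop at clinical progression |
|---|---|
| PFS12, 10% clinical-first | about +1 to +2 points |
| PFS12, 20% clinical-first | +2.4 to +4.9 points |
| PFS12, all 36 | +0.6 to +8.1 points |
| PFS6, all 36 | +0.4 to +6.2 points |
| Median PFS, all 36 | 0 to +3.7 months (coarse: events fall on the scan grid) |

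One middle scenario (median 11 months, 20% clinical-first, 6 months' survival after progression): PFS12 goes from 50.1% to 54.1%.

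**5. Who is censored.** In that scenario, 35% of the patients stopped at clinical progression still count as events through death, at a median of 1.6 months after clinical progression. The other 65% are censored: 47% under the two-missed-visit rule and 18% at the cut-off, with median survival of 9.8 months. Over all scenarios, 17% to 58% stay events and 42% to 83% are censored.

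**6. Against sampling error.** With about 102 patients and PFS12 near 50%, the 95% half-width without censoring is 1.96 × √(0.5 × 0.5 / 102) = 1.96 × 0.0495 = 9.7 points. The bias at 10% to 20% clinical-first is smaller than this, but it has one direction and the confidence interval does not show it.

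**The case against.** **The row does not clearly order a stop.** Its second clause runs to confirmed radiological progression, and the phrase about whichever comes first belongs to that list, which omits clinical progression. The row also says that patients who stop drug for non-RECIST reasons should go on being scanned, and that group includes those who stopped for clinical progression. A reader might infer that Table 2 plainly tells sites to stop on the day of clinical progression; the full sentence does not support that. What remains is a mandatory rule with two readings, one of which conflicts with the rest of the plan.

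**The other sections are not absolute.** Appendix F and the SAP allow for feasibility, and only the synopsis and section 4.1 name clinical progression. This stands: no wording will recover every scan. But those allowances excuse scans that cannot be done; they do not end scanning that can.

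**Some scans will be available anyway.** Table 2 refers to scans under standard practice after progression, its footnote d collects local CT/MRI readings after disease progression, and SAP 3.3 uses unscheduled RECIST assessments. These may reduce the bias. The simulation compares two extremes, and the documents establish neither.

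**PFS is secondary and descriptive.** This is correct, and it limits the severity.

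**Conclusion.** The inconsistency is real and should be fixed. On its first clause, Table 2 permits a scan stop that the synopsis and sections 4.1, 7.1.1 and 7.1.3 do not. Where it is followed, PFS6, PFS12, median PFS and duration of response are biased upward. PFS6 and PFS12 rose in all 36 assumed scenarios. The primary endpoint and OS are unaffected.

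The size depends on how often clinical progression comes first and on survival afterwards, and the documents give neither. The simulated figures show a plausible order of magnitude, conditional on the assumptions listed, and are not an estimate for this trial.

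Two stronger readings are tempting. A reader might infer that the sickest patients become censored. SAP 3.3.1 does not support that: deaths inside the window remain events, so the patients lost are those who live longer after clinical progression. A reader might also infer that the bias is larger in frailer patients; nothing in the documents establishes this.

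**What to change.** **Protocol and sites.** Reconcile the Table 2 tumor-assessment row with sections 4.1, 7.1.1 and 7.1.3 by removing clinical progression or deterioration as a scan stop. Keep the row's existing stops for end of study, death, study discontinuation and Sponsor decision, and merge the two clauses so that only one reading is possible. Send sites a clarification.

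**SAP.** Report, overall and by cohort, how many patients stopped scanning at clinical progression without RECIST progression. Add a PFS sensitivity analysis that counts clinical progression as an event, dated at clinical progression where recorded and otherwise at treatment discontinuation for that reason. This is useful even if much of the follow-up is already complete.

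**Cost.** One corrected row, one letter, one count and one extra analysis. No scans are added beyond those that sections 4.1 and 7.1.3 already specify. The sensitivity analysis reaches only patients with a recorded date or reason: the visible text shows no dated field for patients who stop drug for another reason and decline later. Some scans will remain infeasible.
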